9. PHARMACOKINETIC ANALYSES

Plasma concentrations in relugolix will be summarized and listed.

For patients from China and patients from Japan in the pharmacokinetic subset, pharmacokinetic parameters C_{\max} , $AUC_{0-\tau}$, and t_{\max} from Day 1 and Week 2 Day 1 visit will be determined.

A separate SAP will be detailed for further population pharmacokinetic analyses.

10. SAFETY ANALYSES

Unless otherwise specified, safety analyses will be conducted using the safety population according to the treatment actually received.

10.1. Adverse Events

Per protocol, adverse event reporting period refers to adverse events planned to be collected from the time of the first dose of study drug through the safety follow up visit approximately 30 days after the end of treatment period, or the date of initiation of another investigational agent or hormonal therapy or surgical intervention following the end of treatment, whichever occurs first. Serious adverse events reported to the investigator after the safety reporting period should be reported to the sponsor if the investigator assesses the event as related to the study drug treatment.

The severity of all treatment-emergent adverse events will be evaluated by the investigator based on the National Cancer Institute's Common Terminology Criteria for Adverse Events (NCI CTCAE v4.03) and will be coded to preferred term and system organ class using the Medical Dictionary for Regulatory Activities (MedDRA) 22.0 or higher.

Treatment-emergent adverse event is defined as any adverse event that occur after administration of the first dose of study drug and prior to the end of the adverse event reporting period, except for drug related serious adverse events.

Adverse event summaries will be based on treatment emergent adverse events, unless otherwise specified. Any procedure-related adverse event reported during screening will be listed and flagged in listings by patient.

Tabular summaries with the number and percentage of patients with the following adverse events (but not limited to) will be provided:

- Overview of adverse events
- All adverse events
 - By system organ class and preferred term
 - By decreasing frequency of preferred term
 - By system organ class, preferred term, and maximum severity
 - Study drug-related per investigator by system organ class and preferred term
- Grade 3 or higher adverse events
 - By system organ class and preferred term
 - By decreasing frequency of preferred term
 - Study drug-related per investigator by system organ class and preferred term
- Adverse events leading to study drug withdrawn
 - By system organ class and preferred term
 - By decreasing frequency of preferred term

- Adverse events leading to study drug interruption
 - By system organ class and preferred term
 - By decreasing frequency of preferred term
- Adverse events resulting in fatal outcome
 - By decreasing frequency of preferred term
- Serious adverse events
 - By system organ class and preferred term
 - By decreasing frequency of preferred term
 - By system organ class, preferred term, and maximum severity
 - By system organ class, preferred term, and relationship to study drug
- Adverse events of clinical interest (alanine aminotransferase [ALT] or aspartate aminotransferase [AST] $\geq 3 \times$ upper limit of normal [ULN])
 - By decreasing frequency of preferred term
 - By system organ class, preferred term, and maximum severity

In addition, adverse event categories defined in [Table 7](#) will be summarized by decreasing frequency of preferred term.

Table 7: Constitution of Adverse Event Categories

Category	Search Criteria
Loss of bone mineral density	Osteoporosis/Osteopenia SMQ (broad) All PTs including the term “Fracture,” excluding “Tooth fracture” and “Fracture of penis”
QTc prolongation	Torsades de Pointes/QT prolongation SMQ (broad)
Hepatic transaminase elevations	Drug-related hepatic disorders SMQ (narrow)
Carbohydrate and lipid metabolic effects	Dyslipidaemia SMQ (broad) Hyperglycemia/New onset diabetes mellitus SMQ (narrow)
Adverse Cardiovascular events	Major Adverse Cardiovascular Events: Myocardial infarction SMQ (broad) Central nervous system haemorrhages and cerebrovascular conditions SMQ (broad) Deaths due to all causes Ischemic heart disease Ischaemic heart disease SMQ (broad)

Vasomotor symptoms	The following 5 PTs will be included: 1. Hyperhidrosis 2. Feeling hot 3. Hot flush 4. Night sweats 5. Flushing
Mood Disorders	Depression and suicide/self-injury SMQ (broad)
Hypersensitivity	Hypersensitivity SMQ (narrow)

Abbreviations: PT = preferred term; SMQ = Standardised MedDRA Queries.

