4.4.2. Adverse Events

The imputation rule for the safety analyses will be used to address the issues with partial dates. The imputed dates will be used to determine the treatment-emergent period. For adverse events with a partial date, available date parts (year, month, and day) of the partial date will be compared with the corresponding date components of the start date and end date of the treatment-emergent period to determine if the event is treatment emergent. When in doubt, the adverse event will be considered treatment emergent by default. The following rules will be applied to impute partial dates for adverse events:

If start date of an adverse event is partially missing, impute as follows:

- If both Month and Day are missing and Year = Year of treatment start date, then set to treatment start date, as long as adverse event end date is not prior to treatment start date;
- If both Month and Day are missing and Year \neq Year of treatment start date, then set to January 1;
- If Day is missing and Month and Year = Month and Year of treatment start date, then set to treatment start date, as long as adverse event end date is not prior to treatment start date;
- If Day is missing and Month and Year \neq Month and Year of treatment start date, then set to first of the month;
- If start date is completely missing, set to treatment start date, as long as adverse event end date is not prior to treatment start date.

If end date of an adverse event is partially missing, impute as follows:

- If both Month and Day are missing, then set to December 31;
- If only Day is missing, then set to last day of the month;
- If end date is completely missing, do not impute.

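### The treatment-emergent definition in SAP Section 10.1 is miswritten: read literally it excludes drug-related serious adverse events, and the likelier intended meaning leaves those events without a per-patient end date

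*SAP*

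**What the plan says.** SAP Section 10.1 (Adverse Events) does four things that bear on this point.

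- It sets the reporting period from first dose "through the safety follow up visit approximately 30 days after the end of treatment period". The period closes earlier if the patient starts another investigational agent, hormonal therapy or surgical intervention after treatment ends.
- It adds a rule for late events, limited to those judged drug-related: "Serious adverse events reported to the investigator after the safety reporting period should be reported to the sponsor if the investigator assesses the event" in that way. No time limit is given.
- It defines a treatment-emergent event as any event after the first dose and "prior to the end of the adverse event reporting period, except for drug related serious adverse events".
- It makes that set the default for the tables: "Adverse event summaries will be based on treatment emergent adverse events, unless otherwise specified".

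The planned tables that follow include serious events "By system organ class, preferred term, and relationship to study drug". For all events and for Grade 3 or higher events they include a table headed "Study drug-related per investigator by system organ class and preferred term".

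SAP Section 4.4.2 classifies partially dated events by comparing the available date parts with the "start date and end date of the treatment-emergent period to determine if the event is treatment emergent".

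**The concern.** The exception is attached to the definition without saying what it modifies. By ordinary grammar it removes drug-related serious events from the set. A programmer who follows the sentence would flag a related serious event in mid-treatment as not treatment-emergent. It would then be missing from the all-event, Grade 3 or higher, fatal and serious summaries and from the Table 7 categories.

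A programmer who reads the sentence together with the late-reporting rule would do the opposite. That programmer would keep every related serious event and go on counting them after the window has closed for everything else. Both could claim to have followed the SAP, and their serious, fatal and Grade 3 or higher counts could differ. These counts are central to the adverse event comparison in a registration trial.

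**Working it through.** No arithmetic applies, because the question is what the definition admits. The SAP states no figure to reproduce.

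**Step 1. Classify four kinds of event under each reading.** The examples are illustrative.

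| Event | Literal reading | End-date exemption only | Onset-date rule (proposed) |
|---|---|---|---|
| Related, serious, on treatment | Out | In | In |
| Unrelated, serious, on treatment | In | In | In |
| Related, serious, after the period | Out | In, up to data cut-off | Separate summary |
| Unrelated, serious, after the period | Out | Out | Out |

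**Step 2. Test the literal reading against the planned tables (Section 10.1).** With related serious events removed, the serious-event table by relationship has nothing in its related category. The drug-related table for Grade 3 or higher events, and the one for all events, would hold only non-serious events. None of the listed adverse event tables states a different event set, so the default applies to them. The literal definition and the table plan cannot both stand.

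**Step 3. Test the end-date exemption.** This reading fits the late-reporting rule and the planned tables, but three things remain unsettled.

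- *Window.* Section 4.4.2 needs an end date for the treatment-emergent period. For related serious events this reading supplies none at patient level. The remaining limit is the study-level data cut-off. Section 3.2 places the second cut-off of the primary analysis at the last safety follow-up visit, so the time available after a patient's own period ends depends on when he enrolled or stopped.
- *Later therapy.* The reporting period closes when another investigational agent, hormonal therapy or surgical intervention begins. The exemption overrides that closure, so a related serious event during later therapy could count as treatment-emergent.
- *Causality.* Related and unrelated serious events would have different windows. The investigator's judgement decides which applies, and Section 2.1 describes the trial as open-label. Attribution would then affect overall serious-event incidence as well as the related column.

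**Step 4. Check the reach.** Laboratory and liver-test tables (Section 10.2) and vital-sign tables (Section 10.3.3) are built on baseline and postbaseline measurements, not on the treatment-emergent flag. They do not change under either reading.

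**The case against.** The strongest reply is that the intent is plain. The exception comes straight after the end of the reporting period and echoes the late-reporting rule earlier in the section. The relationship table and the drug-related tables make sense only if related serious events are included. On this view, the fact that the literal reading empties a planned table shows that nobody meant it. This stands as an argument about intent: a reader might infer that the sponsor plans to drop related serious harm, and the document does not support that. It does not repair the sentence, which still says something else.

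A reader might also infer that these events vanish from every safety table, or that late events run on without any limit. Neither follows. Step 4 shows which outputs are untouched, the adverse event summaries carry a clause allowing other specifications, and the data cut-off bounds late events administratively.

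A third reply is that the dependence on causality starts with collection: after the period, the SAP calls for serious events to be reported only if judged related. That is correct, and the proposed change does not remove the dependence. It only keeps causality-selected events out of the main between-arm incidence. Moving them is a choice of presentation, which the SAP does not compel.

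Finally, Section 4.4.2 treats doubtful cases as treatment-emergent. That helps with incomplete dates, but it does not settle what the definition includes.

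**Conclusion.** The concern holds as a defect of definition. The sentence as written contradicts the table plan of its own section. The reading that removes the contradiction is not stated, and it lacks a per-patient end date. Severity is moderate: the adverse event summaries are affected, but no primary or alpha-protected efficacy analysis depends on the clause.

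The size cannot be derived from the SAP, which gives no rate of related serious events. As an assumption only, suppose 1% to 3% of patients have one. The literal reading would then remove 610 × 0.01 to 610 × 0.03, about 6 to 18 relugolix patients, and 305 × 0.01 to 305 × 0.03, about 3 to 9 leuprolide patients. These figures use the planned group sizes and apply only to the less likely reading. For the likelier reading, the number of related serious events between the end of a patient's period and the cut-off is unknown, and no change in any comparison has been shown. The conclusion rests on the wording and on none of these figures.

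**What to change.** Replace the definition in Section 10.1 with a rule on onset date alone, for example: *A treatment-emergent adverse event is any adverse event, whatever its seriousness or relationship to study drug, with onset after the first dose and no later than the close of the adverse event reporting period. Related serious adverse events with onset after that close, up to the data cut-off, are presented in a separate summary and listing by treatment arm.*

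Both arms and both causality categories then share one rule for the main tables. Section 4.4.2 has the end date it needs, the relationship table can be filled as planned, and the late related events remain visible.

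The cost is one rewritten sentence, one derivation flag and one small extra table with its listing. The downside is that late related serious events leave the main tables. If the sponsor prefers to keep them there, the SAP should say so and state the date up to which they count for each patient.

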10.2. Laboratory Data

Laboratory parameters, including chemistry and hematology panels, specified as per protocol and collected from the central laboratory, will be tabulated and presented in by-patient listings. Urinalysis and hepatitis virus serological test results, if any, will be provided in by-patient listings only.

The NCI CTCAE grading scale with numeric component will be used to categorize toxicity grade for laboratory parameters (CTCAE v4.03). Parameters that have criteria available for both low and high values (eg, hypercalcemia for a high value of calcium and hypocalcemia for a low value of calcium) will be summarized for both criteria (low and high). Patients will only be counted once for each criterion. The same patient can be counted for both criteria if the patient has laboratory values meeting each criterion. Shift tables will be provided for each gradable parameter to summarize baseline toxicity grade versus worst postbaseline toxicity grade. For laboratory parameters that are not gradable by the CTCAE, a shift table based upon the normal range (low, normal, and high) will be provided for each parameter to summarize the baseline versus worst postbaseline results.

Boxplots of laboratory values over time will be plotted for key laboratory parameters. These laboratory parameters include but are not limited to hematology (hemoglobin, platelets, leukocytes, neutrophils), creatinine, glomerular filtration rate, and hepatic function panel (ALT, AST, ALP, and total bilirubin [TBL]).

The change from baseline to each postbaseline study visit will be presented by treatment group for each laboratory test.

The number and proportion of patients with liver test elevations will be presented by treatment group. Liver test elevations are assessed by using postbaseline results for ALT, AST, ALP, and TBL based on the definitions presented in [Table 8](#).

Table 8: Categories of Liver Function Test Elevations

Laboratory Test	Category
ALT or AST	ALT or AST > ULN - < 3 × ULN ALT or AST ≥ 3 × to < 5 × ULN ALT or AST ≥ 5 × to < 8 × ULN ALT or AST ≥ 8 × to < 10 × ULN ALT or AST ≥ 10 × to < 20 × ULN ALT or AST ≥ 20 × ULN
Total bilirubin	Total bilirubin > 2 × ULN
ALT or AST and total bilirubin	ALT or AST ≥ 3 × ULN + total bilirubin > 2 × ULN
ALT or AST, total bilirubin, and ALP	ALT or AST ≥ 3 × ULN + total bilirubin > 2 × ULN + ALP < 2 × ULN

Abbreviations: ALP = alkaline phosphatase; ALT = alanine aminotransferase; AST = aspartate aminotransferase; ULN = upper limit of normal.

The number and percent of patients with either ALT or AST ≥ 3 times the ULN and TBL > 2 times ULN concurrently, defined as measurements occurred on the same day, will also be presented.

Worst postbaseline ALT and TBL values will be evaluated using the evaluation of drug induced serious hepatotoxicity (eDISH) concept.

Selected chemistry and hematology test results meeting pre-defined limits of change at any time and based on last observation on treatment will be also summarized per pre-defined threshold (refer to [Appendix 2](#)).

10.3. Other Safety Analyses

10.3.1. Electrocardiograms

Electrocardiogram assessment will be read by local reading. Overall interpretation will be presented in by-patient listing.

10.3.2. Visual Acuity

Visual acuity will be measured using the tumbling E chart with Visual Acuity Score. A 10-foot standard distance will be used and each correctly identified “E” will increase the Visual Acuity Score by one point. Visual Acuity Score at baseline and at each scheduled postbaseline assessment time point will be presented in by-patient listing. Visual acuity score ≤ 90 or decrease from baseline ≥ 10 points will be flagged in the by-patient listing.

10.3.3. Vital Signs

Blood pressure (systolic and diastolic), heart rate, and weight measurements will be summarized at baseline and each subsequent scheduled assessment by treatment group. Change from baseline will be calculated and presented for each parameter at all scheduled postbaseline assessment timepoints. All vital sign data will also be provided in by-patient listing.

Potentially clinically significant abnormalities in vital signs are defined in [Table 9](#) and will be summarized by treatment group. Potentially clinically significant abnormalities will also be flagged in by-patient listing.

Table 9: Categories of Potentially Clinically Significant Abnormalities in Vital Signs

Vital Sign Parameter	Category
Systolic blood pressure	≥ 140 mmHg
	≥ 180 mmHg
	≤ 90 mmHg
	Increase of ≥ 20 mmHg from baseline Decrease of ≥ 20 mmHg from baseline
Diastolic blood pressure	≥ 90 mmHg
	≥ 105 mmHg
	≤ 50 mmHg
	Increase of ≥ 15 mmHg from baseline Decrease of ≥ 15 mmHg from baseline
Heart rate	≥ 120 bpm
	< 45 bpm
	Increase of ≥ 15 bpm from baseline Decrease of ≥ 15 bpm from baseline

REFERENCES

REVISION HISTORY

Table 10: Revision History

Version	Effective Date	Comments
1.0	12SEP2019	New document
2.0	29OCT2019	
 1. Naming change from “time to castration resistance” to “castration resistance free survival”. 2. Updates on Kaplan-Meier analysis for the primary endpoint, sustained castration rate from Week 5 Day 1 to Week 49 Day 1, to align with FDA review comments in Sections 7.3.1.1, 7.3.1.2, 7.3.2.2 and 7.3.2.3. 3. Corrections in test statistics of difference in cumulative incidence curve at a fixed time point in Section 7.4.3.1. 4. Censoring rule b of analysis on sustained profound castration changed to align with sustained castration rate in Section 7.4.3.2.
3.0	06NOV2019	
 1. Aligned with FDA review comments, changed ≤ 50 ng/dL to < 50 ng/dL for castration level and changed ≤ 20 ng/dL to < 20 ng/dL for profound castration level. 2. To address FDA review comments, added “sustained profound castration rate from Week 5 Day 1 through Week 49 Day 1 as a secondary endpoint, in Table 1, Sections 7.4.2 and 7.4.3.2. 3. To address FDA review comments, similar censoring rules for the primary analysis of sustained castration rate applied to sustained profound castration rates in Section 7.4.3.2.

APPENDIX 1: LIST OF MEDICATIONS THAT HAVE IMPACT ON TESTOSTERONE OR PROSTATE-SPECIFIC ANTIGEN LEVEL

The following lists of medications that are likely to affect analysis of efficacy are identified and will be finalized prior to the database lock. Any changes in this appendix after the finalization of the SAP will not be considered as changes in the planned analysis.

Appendix Table 1: Medication List of Therapies Known to Suppress Testosterone

Generic Name	WHO Drug Dictionary Preferred Term
degarelix	DEGARELIX
	DEGARELIX ACETATE
goserelin	GOSERELIN
	GOSERELIN ACETATE
leuprolide	LEUPROLIDE
leuprorelin	LEUPRORELIN
	LEUPRORELIN ACETATE
abarelix	ABARELIX
histrelin	HISTRELIN
triptorelin	TRIPTORELIN
	TRIPTORELIN ACETATE
	TRIPTORELIN EMBONATE

Appendix Table 2: Medication List of Treatments that Can Affect or Alter Prostate-Specific Antigen

Generic Name	WHO Drug Dictionary Preferred Term
cabazitaxel	CABAZITAXEL
cisplatin	CISPLATIN
docetaxel	DOCETAXEL
doxorubicin	DOXORUBICIN
	DOXORUBICIN HYDROCHLORIDE
etoposide	ETOPOSIDE
fluorouracil	FLUOROURACIL
ifosfamide	IFOSFAMIDE
paclitaxel	PACLITAXEL
bicalutamide	BICALUTAMIDE
chlormadinone acetate	CHLORMADINONE ACETATE
enzalutamide	ENZALUTAMIDE
flutamide	FLUTAMIDE
nilutamide	NILUTAMIDE
epalutamide	EPALUTMIDE
estramustine	ESTRAMUSTINE
sipuleucel-T	SIPULEUCEL-T

APPENDIX 2: LIST OF PRE-DEFINED THRESHOLD IN SELECTED CHEMISTRY AND HEMATOLOGY TEST RESULTS

Chemistry Laboratory	
Liver Function	
ALT > ULN and < 3X ULN	Total BILI > ULN
ALT >= 3X ULN and < 5X ULN	Total BILI > 2X ULN
ALT >= 5X ULN and < 10X ULN	
ALT >= 10X ULN and < 20X ULN	ALT or AST >= 3X ULN and Total BILI > 2X ULN
ALT >= 20X ULN	ALT or AST >= 3X ULN and Total BILI > 2X ULN and ALP < 2X ULN
	ALT > ULN and < 3X ULN
AST > ULN and < 3X ULN	
AST >= 3X ULN and < 5X ULN	GGT > ULN and < 3X ULN
AST >= 5X ULN and < 10X ULN	GGT >= 3X ULN and < 5X ULN
AST >= 10X ULN and < 20X ULN	GGT >= 5X ULN and < 10X ULN
AST >= 20X ULN	GGT >= 10X ULN and < 20X ULN
	GGT >= 20X ULN
ALT or AST > ULN and < 3X ULN	GGT > ULN and < 3X ULN
ALT or AST >= 3X ULN and < 5X ULN	
ALT or AST >= 5X ULN and < 10X ULN	
ALT or AST >= 10X ULN and < 20X ULN	
ALT or AST >= 20X ULN	
Renal Function	
CR > 1.5 mg/dL and > BL	GFR < 15 mL/min per 1.73 m ²
CR > 50% increase from BL	GFR >= 15 - < 30 mL/min per 1.73 m ²
	GFR >= 30 - < 60 mL/min per 1.73 m ²
	GFR >= 60 - < 90 mL/min per 1.73 m ²
	GFR >= 90 mL/min per 1.73 m ²

Chemistry Laboratory	
Metabolic Parameters	
Fasting Glucose	Highest Postbaseline Glucose
< 100 mg/dL at BL	Gluc \geq 200 mg/dL
< 100 mg/dL at week 48	Gluc \geq 200 mg/dL and \geq 126 BL
\geq 100 - < 126mg/dL at week 48	Gluc \geq 500 mg/dL
\geq 126 mg/dL at week 48	Gluc \geq 500 mg/dL and \geq 126 BL
\geq 100 - < 126 mg/dL at BL	Total CHOL > 200 mg/dL and > BL
< 100 mg/dL at week 48	Total CHOL increase > 30 mg/dL from BL
\geq 100 - < 126 mg/dL at week 48	
\geq 126 mg/dL at week 48	HDL < LLN and < BL
	LDL > ULN and > BL
\geq 126 mg/dL at BL	TRIG > ULN and > BL
< 100 mg/dL at week 48	
\geq 100 - < 126 mg/dL at week 48	
\geq 126 mg/dL at week 48	
Electrolytes and other Chemistry Parameters	
ALB < LLN and < BL	CK > 2X ULN and > BL
ALB > ULN and > BL	CK > 5X ULN and > BL
	CK > 10X ULN and > BL
ALP > 2X ULN and > BL	
ALP > 5X ULN and > BL	MG < LLN and < BL
ALP > 10X ULN and > BL	MG > ULN and > BL
CA < LLN and < BL	PHOS < LLN and < BL
CA > ULN and > BL	PHOS > ULN and > BL

K < LLN and < BL	NA < LLN and < BL
K > ULN and > BL	NA > ULN and > BL
Hematology Laboratory	
HCT < LLN and < BL	NEUT < LLN and < BL
HCT decrease ≥ 10 from BL	NEUT > ULN and > BL
HGB ≤ 10.5 g/dL and < BL	BASO < LLN and < BL
HGB decrease > 1 g/dL from BL	BASO > ULN and > BL
MCV < LLN and < BL	EOS < LLN and < BL
MCV > ULN and > BL	EOS > ULN and > BL
	EOS > 5% and > BL
WBC < LLN and < BL	
WBC > ULN and > BL	PLT < LLN and < BL
	PLT < $100 \times 10^9/L$ and < BL
LYM < LLN and < BL	PLT > ULN and > BL
LYM > ULN and > BL	
	HbA1c ≥ 6.5 and > BL
MONO < LLN and < BL	HbA1c increase > 1.0 from BL
MONO > ULN and > BL	

BL = baseline; LLN = lower limit of normal; ULN=upper limit of normal.
